The sample size was calculated assuming conventional specifications (power = .80, alpha = .05, two-sided tests) and based on the primary endpoints. The sample sizes were determined to allow for the detection of a 15–percentage point improvement in the primary endpoints, our minimum threshold to consider the intervention to be successful. For the HIV-/u cohort, the current rate of HIV testing is estimated to be about 40%. With a sample size of 200 (each of the three cohorts), The study team will be able to detect a 13 to 14% difference, and even with a loss of 10% of the cohort during follow-up (the grant team achieved a 90% retention rate at 12 months in a recent study of AGYW),²⁸ the study team

will still have the statistical power for a minimum detectable difference in HIV testing of 15%. For the HIV+ cohort, viral load suppression is estimated to be 70 to 75% among AGYW. With a sample size of 175 per cohort, the study team will be able to detect a minimum difference of 15% even with a 10% loss to follow up. See **Exhibit 3** for details on sample size included in the cluster randomized trial.

Exhibit 3. Experimental design and sample sizes*

Post-intervention data collection: We will conduct one post-intervention survey with AGYW at about 24-months from study initiation (approximately 12 months after intervention completion).

Research Protocol

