Cost-effectiveness, budget impact, and policy implications. The study team will use a previously validated instrument, The Cost Assessment Tool,⁶⁰ to create a tailored data collection approach to collect resource use information on the interventions. Our main goal is to estimate the implementation cost of the IWC and the SHIELD interventions from the program perspective (which will reflect MOH resources needed to sustain interventions), but the study team will also derive the start-up costs related to developing the interventions to inform future adaption of these interventions to other settings. The study team will estimate labor hours of IWC clinic staff, PN, and other staff by prospectively tracking time spent by each project staff member implementing the intervention on a pre-defined set of activities and use hourly wage to calculate cost. The study team will also document the expenditure on non-labor resources. Using standard economics methodology,^{61,62} the study team will explore economies of scale that can be achieved during scale-up. The cost information, along with the effectiveness impact of the IWC and SHIELD interventions, will be used as inputs in previously validated models and approaches developed by RTI.⁶³ The study team will evaluate the tradeoff, or return on investment, between investing in HIV prevention and lowering HIV treatment cost over the long term. The usual care (base case) will be compared to the long-term effectiveness of including the IWC clinic-based intervention with and without the SHIELD community-based interventions to address barriers along the continuum of care. The study team will report the projected decrease in HIV incidence,

increase in community-level viral load suppression, and incremental cost per quality-adjusted life years. The study team will conduct policy simulations to assess the impact of scaling up the interventions to the population level; perform sensitivity analysis, varying the range of effectiveness and cost estimates; and generate potential best- and worst-case scenarios. The study team will create tornado and spider diagrams to display this uncertainty assessments graphically to policy makers. This cost-effectiveness analysis will be complemented by a budget analysis, which will identify the financial outlays that will be required annually to implement the intervention during the implementation trial in the scale-up process.

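### The economic plan commits to no joint uncertainty analysis, so its diagrams and scenarios cannot show how likely the package is to be cost-effective

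*Combined protocol and SAP*

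**What the plan says.** Section 3.3 (Combined protocol and SAP), under the heading on cost-effectiveness, budget impact and policy implications, holds all the text on economic uncertainty.

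- **Inputs:** "The cost information, along with the effectiveness impact of the IWC and SHIELD interventions, will be used as inputs in previously validated models".
- **Outputs:** these include "increase in community-level viral load suppression, and incremental cost per quality-adjusted life years".
- **Uncertainty:** the team will "perform sensitivity analysis, varying the range of effectiveness and cost estimates; and generate potential best- and worst-case scenarios".
- **Display:** "The study team will create tornado and spider diagrams to display this uncertainty assessments graphically to policy makers".
- **Scale-up:** "The study team will conduct policy simulations to assess the impact of scaling up the interventions to the population level". These simulations are not described as probabilistic.

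The documents give no input distributions, joint sampling, interval for the cost per QALY, net benefit, acceptability curve or willingness-to-pay threshold.

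The effects that feed the model come from six zones in three groups, two zones each: IWC plus SHIELD, SHIELD only, and control. The analysis-of-hypotheses text in the same section plans GEE models and will assess the need for a small-sample correction. The economic text does not say whether the standard errors from those models reach the economic model.

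**The concern.** Tornado and spider diagrams move one input and hold the rest at base values. Best and worst cases, on the usual reading, push every input to its extreme together. Neither carries the joint error of the testing effect, the suppression effect and the costs into the cost per QALY, and neither has a stated coverage.

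The results are meant for decisions. Objective 3 sends them to national partners, section 3.3.5 plans a policy forum for government officials, and the text under Steps to Minimize Risks foresees Ministry advocacy for national scale-up. Officials would see ranges without knowing how probable they are. If the trial effect is imprecise, the worst-case ratio may not exist at all.

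**Working it through.** **1. The plan's own figure.** The economic text states no number, so I checked the effect size that feeds it. The sample-size text aims at "detection of a 15–percentage point improvement in the primary endpoints". For two proportions without clustering, solve d = 1.96·√(2·p̄(1−p̄)/n) + 0.842·√([p₁(1−p₁)+p₂(1−p₂)]/n):

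- HIV testing from 40%: d = 13.9 points at 200 per arm and 14.7 at 180. The stated 13 to 14, and 15 after 10% loss, reproduce.
- Suppression at 157 per arm (175 less 10%): 13.3 points from 70% or 12.3 from 75%, within the stated 15.

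**2. Standard errors, no clustering.**

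- Testing, 40% vs 55%, 180 per arm: √[(0.40×0.60 + 0.55×0.45)/180] = 5.2 points.
- Suppression, 70% vs 85%, 157 per arm: √[(0.70×0.30 + 0.85×0.15)/157] = 4.6 points.

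**3. Illustration (assumed model).** Ratio = C / (0.5·T/15 + 0.5·V/15), with T and V in points, normal with mean 15, and C gamma with mean 1 and CV 20%, all independent. The equal weights, cost CV and independence are my assumptions. The base value is 1.

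- Cost bar: C from 0.647 to 1.428, so 0.65–1.43.
- Testing bar: T = 15 ± 1.96×5.2 = 4.8 to 25.2, denominator 0.660 to 1.340, so 0.75–1.51.
- Suppression bar: V = 15 ± 1.96×4.6 = 6.0 to 24.0, denominator 0.699 to 1.301, so 0.77–1.43.
- All best: 0.647/1.640 = 0.39. All worst: 1.428/0.360 = 3.97.
- Joint 95% interval (Monte Carlo): 0.56–1.99.

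The cost and testing bars cover about 79% and 73% of the joint distribution.

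**4. Less precise effects.** With SEs of 7.0 and 6.5 points, the joint interval is 0.51–2.74. These SEs imply design effects of (7.0/5.20)² = 1.81 and (6.5/4.64)² = 1.97, or ICCs near 0.81/89 = 0.009 and 0.97/77.5 = 0.012 at 90 and 78.5 per zone. My rerun showed that ranking the roughly 0.08% of draws with a non-positive effect as worst outcomes, instead of leaving their ratios negative, moves the interval to about 0.52–2.78.

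**5. Direction in general.** For k equal independent inputs and an additive outcome, a one-way bar is 1/√k of the joint 95% width and the all-extreme range is √k times it. For k = 2, 5 and 10, the bar is 71%, 45% and 32% of the joint width and covers 83%, 62% and 46%.

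**6. When one input dominates.** Take cost divided by the testing effect alone (15 points, SE 5.2, log-SD of cost 0.15, base 6.67). The effect bar is 3.97–20.8 and the joint interval 3.65–21.5, so almost nothing is lost.

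**7. When the effect interval reaches zero.** With 90 per zone and an assumed ICC of 0.02, the design effect is 1 + 89×0.02 = 2.78, the SE 5.20×√2.78 = 8.7, and the interval −2 to 32 points. At ICC 0.05 the design effect is 5.45, the SE 12.2, and the interval −9 to 39. The worst-case ratio is then undefined. The probability of being cost-effective is still computable: at an arbitrary threshold of 10 with log-SD of cost 0.30, it is 0.69 and 0.64.

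**The case against.** The strongest reply is that the gap is one of silence. The plan does not say its sensitivity analysis is one-way only, the scenarios are undefined, and the existing models it relies on may already include a probabilistic step. This is fair: a reader might infer that joint analysis is excluded, and the text does not support that. What stands is that the plan commits to none and that the one display it names is a one-at-a-time display.

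Four other stronger readings also fail.

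- **Effect uncertainty is the main driver.** Not shown. In the unclustered illustration the cost bar is as wide as the testing bar (0.78 against 0.77). If one effect did dominate, the shortfall would shrink, as step 6 shows.
- **The scenarios are wrong because they are wide.** The plan says it will "generate potential best- and worst-case scenarios". These are bounding cases and are not offered as 95% intervals. The fair complaint is that they have no stated coverage.
- **Objective 3 asks for the probability of being cost-effective.** It asks for cost-effectiveness and budget analysis to describe impact along the care continuum. The probability is what a decision maker would want, but it is not the stated question.
- **The widest bar is 0.65–1.51.** No single bar is. That range joins the low end of the cost bar to the high end of the testing bar.

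It is also true that the illustration is not the planned QALY model, and that this is a secondary objective that could be dealt with in a later economic analysis plan.

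**Conclusion.** The concern holds as a gap in method. The plan commits to no analysis that carries the joint uncertainty of trial effects and costs into the cost per QALY, so it cannot show how likely the package is to be cost-effective. One-at-a-time bars are too narrow when several independent inputs matter, and a worst-case ratio fails if the cluster-adjusted effect interval reaches zero.

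The documents support the direction and not the size, because they give no costs, ICC or threshold. The illustrative contrast, with bars covering about 79% and 73% of the joint distribution, rests on equal weights, a 20% cost CV, independence and no clustering. It would be smaller with one dominant input. The primary endpoint tests are not affected. This is a cheap and worthwhile improvement to a stated objective.

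**What to change.** In the cost-effectiveness text of section 3.3:

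1. **Make a probabilistic sensitivity analysis the main uncertainty result.** Draw the arm effects jointly from the cluster-adjusted, small-sample-corrected estimates, and draw costs and other inputs from stated distributions.
2. **Allow for the few zones.** Six zones give a poorly estimated covariance. Use t-type draws rather than normal ones and repeat over a range of ICCs. A zone-level comparison has 6 − 3 = 3 degrees of freedom, so a 95% multiplier of 3.18 instead of 1.96.
3. **Report net benefit with intervals, and acceptability curves over a stated range of thresholds,** for the three randomised arms (IWC plus SHIELD, SHIELD only, control).
4. **Reconcile the comparators.** The economic text compares usual care with IWC both with and without SHIELD, but the randomised design has no IWC-only arm, so the trial gives no direct estimate for that option.
5. **Keep the tornado and spider diagrams and the scenarios as supplements,** to show which inputs drive the result.

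The cost is about a paragraph of text and more model runs, with no new data or visits. The timeline in Exhibit 5 places model finalisation and policy simulations in Year 5. The price is that reported ranges will be wider than the one-way bars.

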4.0 Data Management

Research materials obtained from individuals recruited into this study will include the following:

- Consent forms
- Contact information sheets (“locator forms” and eligibility assessments)
- Audio files and transcripts of interview and focus group sessions
- Completed surveys
- Clinic data (through clinic data abstractions)
- Intervention tracking details on education sessions and services provided

All participant data will be managed according to Zambian and U.S. regulations (45 CFR part 46) and ICH-GCP. Participants will receive a unique study identification number (PTID) that will be recorded on all study forms and interview transcripts. PTIDs will be maintained by the Population Council Field Coordinator, and a Screening and Enrollment Log will provide a link between participant name and PTID. The Screening and Enrollment Log will be stored in a secure, double-locked location in the Field Coordinator’s office,

separate from participant data. Hard-copy (paper) consent forms and contact information sheets containing personally identifying information will likewise be stored in a secure, limited-access location separate from participant data. Personal identifying information will be accessible only to key study personnel and will not be transmitted to RTI.

All other data (transcripts) will be coded by PTID and will not contain any personal identifiers. The qualitative transcripts and audio files will be maintained as electronic records, which will be stored in encrypted, password-protected files, coded by PTID, and transmitted to RTI using a secure file transfer protocol (FTP) server. All electronic data and study databases will be stored on secure, password-protected computers in the project office computers, accessible by key study personnel only.


A study coordinator, from among the existing Population Council staff will be in charge of coordinating data collection. She will be responsible for the day-to-day supervision of PNs; planning and coordination of fieldwork activities.

Approximately 14 PNs will be recruited to the Population Council staff and will be responsible for leading youth club sessions and providing peer navigation across the participating communities. The PNs will have skills in conducting in-depth interviews and focus group discussions, and conversant in the two main local languages (Bemba and Nyanja) spoken in the study site. While many will have previous research

experience, they undergo a training program on conducting SHIELD sessions, stigma, clinic navigation, and research ethics, particularly on research with minors, prior to the start of data collection activities. PNs will also undergo training and receive certification for conducting mobile HIV counseling and testing (HCT) along with pregnancy testing. In addition to the PNs, 2 IWC clinic nurses will be hired to the UNC staff and will be responsible for facilitating the IWC clinic services, including HIV counseling and testing, HIV treatment and adherence counseling, contraception, pregnancy testing, HPV vaccination, along with making referrals for other services requested. The IWC clinic nurses will undergo training and will receive certification for HCT.

In addition to study staff, we have also established a data safety monitoring board (DSMB), which includes 5 Zambian experts or clinicians that work on adolescent health or HIV. The DSMB charter specifies the terms for project oversight, establishes regular DSMB meetings, and specifies the role of the DSMB in data monitoring.

6.0 Timeline

The study timeline is presented in **Exhibit 5**.

Exhibit 5. Project Timeline

| Year 1 | Year 2 | Year 3 | Year 4 | Year 5 |
|--|--|--|--|---|
| 
Months 1–4
 
 • Formalize subcontracts • Prepare IRB materials • Situation assessment 
Months 5–12 (UG3-1)
 
 • Develop and pilot test SHIELD modules • Advisory boards meet • PATC3H meetings 
Consultation forum: MOH & partners
 | 
Months 13–20 (UG3-2)
 
 • Establish sampling frame for AGYW and conduct DCE 
Months 16–24 (UG3-3)
 
 • Pilot test IWC clinic services & protocols • Publish & present formative research | 
Months 25–36 (UH3-1)
 
 • Initiate cluster randomized trial with IWC clinic and SHIELD intervention 
Months 25–36 (UH3-2)
 
 • Initiate clinic staff & peer navigator data collection • Data Safety Monitoring Board meets | 
Months 37–48 (UH3-1 and UH3-2 continued)
 
 • Continue 6- and 12-month follow-up and data analysis; sources include self-report, clinic audit, & biological 
Publish & present interim findings
 | 
Months 49–60 (UH3-3)
 
 • Complete data analysis, finalize model, and conduct policy simulations • Policy forum: MOH & stakeholders • Publish & present final results |

References

1. UNAIDS. (2016). *HIV prevention among adolescent girls and young women*. Retrieved from http://www.unaids.org/sites/default/files/media_asset/UNAIDS_HIV_prevention_among_adolescent_girls_and_young_women.pdf
2. Wong, V. J., Murray, K. R., Phelps, B. R., Vermund, S. H., & McCarraher, D. R. (2017). Adolescents, young people, and the 90-90-90 goals: A call to improve HIV testing and linkage to treatment. *AIDS (London, England)*, 31(Suppl 3), S191–S194. <http://dx.doi.org/10.1097/QAD.0000000000001539>
3. Central Statistical Office (CSO) [Zambia], Ministry of Health (MOH) [Zambia], and ICF International. 2014. Zambia Demographic and Health Survey 2013-14. Rockville, Maryland, USA: Central Statistical Office, Ministry of Health, and ICF International.
4. UNAIDS. (2017, July 19). *HIV estimates with uncertainty bounds 1990-2016*. Retrieved from http://www.unaids.org/en/resources/documents/2017/HIV_estimates_with_uncertainty_bounds_1990-2016
